One of the critical areas where these enzymes show promise is in the modulation of lactate metabolism. Lactate, often produced in higher quantities during intense physical activity, can lead to fatigue and decreased muscle efficiency. The traditional view of lactate as merely a byproduct of anaerobic metabolism has evolved, with current research acknowledging its role as a valuable energy source during prolonged exercise [23]. This shift in understanding opens up new avenues for utilizing enzyme supplementation to optimize lactate utilization. Enzymes such as bromelain and papain, found in pineapples and papayas respectively, have been studied for their potential in improving lactate metabolism. These enzymes are known to facilitate faster clearance of lactate from the bloodstream, thereby enhancing recovery and reducing fatigue [26, 28]. Furthermore, the antioxidant properties of these enzymes play a crucial role in combating oxidative stress, which is often elevated during intense exercise regimes [24, 25]. This reduction in oxidative stress is not only beneficial for immediate recovery but also contributes to long-term muscle health and function. Moreover, the anti-inflammatory actions of these natural enzymes can mitigate the inflammatory response often triggered by high-intensity exercise [27]. By reducing inflammation, these enzymes may enhance muscle recovery and function, thus allowing for more efficient and prolonged exercise performance. This aspect is particularly relevant in training regimens where recovery is as crucial as the exercise itself.

The primary aim of this feasibility study is to examine the effects of fruit and vegetable enzyme supplementation on aerobic capacity and blood lactate response in elderly individuals engaged in HIIE through an exergaming framework. This study is dual-faceted, focusing firstly on the physiological responses and feasibility of an exergaming-HIIE regimen tailored for the elderly, and secondly, on the impact of enzyme supplementation on enhancing these exercise outcomes.

Methods

Participants And Experimental Design

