All participants reported a regular exercise habit (3 times per week within the past year). They also completed the Physical Activity Readiness Questionnaire and confirmed no history of upper limb skeletal muscle injury or major injury. Participants were instructed to avoid strenuous activities and the intake of caffeine or muscle-enhancing supplements for 24 hours prior to the experiment. Before the study commenced, all participants provided personal information, completed health questionnaires, disclosed personal medical history, and signed informed consent forms.

The 16 participants underwent the Exergaming HIIE test as an initial assessment (pre-test). Participants engaged in a 5-minute warm-up on a stationary bike, followed by HIIE using the Nintendo Switch Ring Fit Adventure design. The training method was adapted from the research of [8, 9] and consisted of 8 sets of 20 seconds of

maximum effort exercise with 30 seconds of complete rest between each set, resulting in a total exercise time of 370 seconds. The HIEE design incorporated training modes targeting the deltoid, pectoralis major, latissimus dorsi, and quadriceps muscles in the Nintendo Switch Ring Fit Adventure. Blood lactate levels, heart rate, and ratings of perceived exertion were recorded before, during, and after exercise, and training load was quantified using TRIMP. Participants were matched and divided into two groups, the enzyme group, and the placebo group, based on their blood lactate levels during HIEE. Each group comprised 8 individuals. Supplementation with vegetable and fruit enzymes or maltodextrin commenced three days after the pre-test and lasted for a total of 14 days. On the 14th day, following the completion of supplementation, the participants underwent the Exergaming HIEE test as a post-test.

Ethical Considerations

The human research ethics committee of the local university approved this study, which was also approved by the human research ethics committee of the National Cheng Kung University, Taiwan. (Approval No. NCKU HREC-E-112-419-2). Users volunteered for this study and agreed to participate by signing an informed consent form.

Supplementation Protocol

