After the pre-test, the enzyme group consumed 30 mL of vegetable and fruit enzymes (The contents include needle-leaf cherries, cherries, apples, cranberries, blackberries, black currants, blueberries, beets, broccoli, cabbage, carrots, Concord grapes, cranberries, elderberries, kale, oranges, peaches, papayas, parsley, pineapples, raspberries, red currants, spinach, and tomatoes, etc.) (Enzyme Village, Chiayi, Taiwan) mixed with 150 mL of water twice a day (at breakfast and dinner) for 14 consecutive days. The placebo group followed the same protocol but consumed malt syrup (Amazon, USA) instead until the end of the study. Participants returned to the laboratory each morning to receive the daily supplement, which was administered on-site. Following supplementation, participants reported their dinner intake to the researchers, ensuring compliance with the prescribed supplementation regimen.

Exergaming HIEE Test-Combination Of Exergaming And HIEE

Participants in this experiment engaged in HIEE using the Nintendo Switch Ring-Con within a laboratory environment. All participants completed pre-test and post-test assessments on the same day. The exergame employed in this study was 'Nintendo Switch Fitness Adventure,' which ingeniously blends exercise with an adventure narrative to deliver both physical workouts and gaming enjoyment concurrently. This game is noted for its intuitive, user-friendly interface that accommodates players of all ages. It incorporates a specialized fitness ring -a smart accessory that connects to the Nintendo Switch console. The sensor system utilized two Nintendo controllers: one mounted on the exercise ring and the other secured to the participant's thigh to enhance gameplay interaction. Through the Ring-Con, participants engaged in diverse physical activities such as weightlifting, yoga, and aerobic exercises. The fitness ring sensor accurately captures and integrates players' movements into the game. The gameplay involves unlocking levels and engaging in fitness challenges that are achieved through actual physical activities. It offers a wide range of exercise routines targeting various

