muscle groups and provides engaging gaming challenges. The exercise protocol included eight sets of 20-second high-effort exercises, interspersed with 30-second rest intervals, totaling 370 seconds of active exercise time. Specifically, the fitness game mode used was the Adventure Mode in 'Ring Fit Adventure,' comprising exercises targeting the pectoralis major, latissimus dorsi, deltoids, and quadriceps muscles (Figures 2).

[figure not shown]

Figure 2. Experimental flowchart. Ex-: bout of HIIE test; Post-5 min: after 5 minutes of HIIE test; Post-10 min: after 10 minutes of HIIE test. Asterisk (*) indicates lactate test. Asterisk (#) indicates test heart rate and RPE.

Blood Lactate Test

The blood lactate was measured at five time points: before exercise, after the fourth and eighth bouts of exercise, and at 5 and 10 minutes after exercise. The blood lactate were analyzed using a Biosen Cline blood analysis system (EKF-diagnostic, Germany). Capillary blood samples of 10 μ L were collected and added to red blood cell lysis reagent and stored at low temperature until analyzed. Prior to analysis, instrument standardization and test calibration were performed, and the coefficient of variation was determined to be $\leq 1.5\%$. The detection range for blood lactate was 0.5-40 mM [31].

Training Impulse

In this study, the exercise load was represented by the TRIMP [32], which is calculated as the product of exercise intensity and duration. To accommodate the convenience of the experiment, two different TRIMP calculation methods were used, including % HRmax (objective) and RPE (subjective). At the end of each exercise bout (8 bouts in total) and during the recovery period before the next bout (7 bouts in total), participants were asked to report their RPE, and their heart rate was recorded. This process was repeated 8 times.

% HRmax Calculation Method

During the entire HIIE, the participant's HR was recorded every 5 seconds using a heart rate monitor (iHeart Polar, Taiwan) to calculate % HRmax. The block TRIMP

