method developed by S. Edwards [33] was used, which divides the exercise intensity into 5 blocks with corresponding weighting factors (Table 1). The weighted score of each block was multiplied by the exercise time (min) and then summed to obtain the exercise load (arbitrary unit [AU]). The calculation formula is as follows: Exercise load = (Z1 exercise time × 1) + (Z2 exercise time × 2) + (Z3 exercise time × 3) + (Z4 exercise time × 4) + (Z5 exercise time × 5)

Table 1 The Edwards' block TRIMP calculation method

Zone	Intensity	Weighted score
Z1	50%-60% HRmax	1
Z2	60%-70% HRmax	2
Z3	70%-80% HRmax	3
Z4	80%-90% HRmax	4
Z5	90%-100% HRmax	5

RPE Calculation Method

The TRIMP calculation method of Foster, Hector [34] and Foster, Florhaug [35] was used to calculate the exercise load by multiplying the RPE value of each exercise segment by the exercise time and summing them up. The RPE scale used in this method was the CR-10 version modified by Foster, Florhaug [35] based on Borg, Ljunggren and Ceci [36] (Table 2). The calculation formula is as follows: Exercise load (AU) = Borg's CR-10 RPE score × exercise time (min)

Table 2. Borg's CR-10 RPE

0	Rest
1	Very, very easy
2	Easy
3	Moderate
4	Somewhat Hard
5	Hard
6	
7	Very Hard
8	
9	
10	Maximal

Statistical Analysis

All the data were analyzed by SPSS for Windows 20.0. Data are expressed as the mean \pm standard deviation (SD) and 95% confidence interval (95% CI). A mixed design two-way analysis of variance (ANOVA) (group \times time) was used to compare the variables of lactate, heart rate and training impulse between two groups before and after the 14-days of supplementation. Graphs were generated using GraphPad Prism 8.0 (GraphPad Software, San Diego, California, USA). Cohen's conventions for ES (Cohen d) were calculated by the G*Power 3.1 software program (Heinrich-Heine-Universität, Düsseldorf, Germany), where the ESs of 0.2, 0.5, and 0.8 are considered small, medium, and large, respectively. Statistical significance was set as $p < 0.05$.

References

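### The allocation rule is only to match and divide on pre-test lactate; with no random draw, concealment or masking stated, a supplement effect cannot be securely attributed

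*Combined protocol and SAP*

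**What the plan says.** Under Participants And Experimental Design, all 16 participants take the exergaming test first. Then "Participants were matched and divided into two groups, the enzyme group, and the placebo group, based on their blood lactate levels during HIEE", with 8 in each group. Supplementation "commenced three days after the pre-test and lasted for a total of 14 days". Nothing more is said about how a participant came to be in one group or the other.

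The matching value is not fixed. Under Blood Lactate Test, "The blood lactate was measured at five time points: before exercise, after the fourth and eighth bouts of exercise", with two further readings in recovery. The allocation sentence refers only to lactate during the test, so the reading after bout 4, the reading after bout 8 or some summary would all fit.

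Under Supplementation Protocol, "Participants returned to the laboratory each morning to receive the daily supplement, which was administered on-site". The comparator is called a placebo, but no section says that the two products look or taste alike, who knows the group, or whether the staff who hand out the product also run the tests.

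The end of the Introduction gives the purpose: "The primary aim of this feasibility study is to examine the effects of fruit and vegetable enzyme supplementation on aerobic capacity" and on the blood lactate response. The Statistical Analysis section plans a mixed two-way ANOVA "to compare the variables of lactate, heart rate and training impulse between two groups before and after the 14-days of supplementation", with no term for the matching.

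**The concern.** Matching settles who is comparable with whom. It does not settle which member of a match receives the enzyme product. Here the groups are formed after every pre-test result is known, so whoever divides the pairs could choose. Matching on lactate leaves age, sex, fitness, heart-rate response and motivation free to differ between the groups.

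A second route opens after allocation. The test consists of "maximum effort exercise with 30 seconds of complete rest between each set". Someone who knows the group can push harder, or be urged to, and lactate and heart rate then follow the effort however accurately they are read. One of the two training-impulse methods also rests directly on self-report: "participants were asked to report their RPE, and their heart rate was recorded". With one morning hand-over per participant per day there are up to 16 × 14 = 224 occasions on which the group could become known to staff. That count shows opportunity, not that bias occurred.

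The pre/post comparison removes a stable baseline difference between groups. It does not remove a difference in change that comes from selection or expectation, and that difference is what the group by time term tests.

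**Working it through.** **1. Reading the text.** There is no stated figure to reproduce; the plan gives no power, SD or effect size. The whole document was read for random assignment, sequence generation, concealment and masking. The allocation sentence is the only relevant text. The words for a double-blind randomised design occur only in the title of a cited study (reference 30). Figure 2 is not shown; its legend lists test times and which measurements are taken at them.

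**2. How much a spurious difference matters at this size (illustration).** Inputs from the plan: 8 per group and a 5% significance level. Assumptions: a two-sided test (sidedness is not stated) and one change score per participant. With two levels of time, the interaction test is then the unpaired t test on change, with 16 − 2 = 14 df. The plan does not define the levels of time and there are five lactate readings per test, so this is a simplification.

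Suppose the supplement does nothing but the groups differ by b SD in expected change. The noncentrality is b × √(8/2) = 2b. The chance of p < 0.05 is:

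| b (SD, assumed) | 0 | 0.25 | 0.35 | 0.5 | 0.8 |
|---|---|---|---|---|---|
| False-positive rate | 5% | 7.5% | 10% | 15.4% | 32.0% |

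**3. Where such a shift could come from (illustration).** Take 8 pairs matched perfectly on lactate. In each pair the member higher on some other trait receives the enzyme product with probability p, and the trait correlates ρ with change. The higher and lower of two independent standard normal values differ on average by 2/√π = 1.128 SD, so the shift is (2p − 1) × 1.128 × ρ. For p = 0.75 and ρ = 0.3 this is 0.5 × 1.128 × 0.3 = 0.17 SD. Rejection rates come from 400,000 simulated trials per setting.

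| ρ (assumed) | p = 0.5 (random) | p = 0.75 | p = 1.0 (worst case) |
|---|---|---|---|
| 0.1 | 5.0% | 5.1% (shift 0.06) | 5.5% (shift 0.11) |
| 0.3 | 5.0% | 6.1% (shift 0.17) | 9.6% (shift 0.34) |
| 0.5 | 5.0% | 8.2% (shift 0.28) | 18.5% (shift 0.56) |

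A random draw within pairs removes this component altogether.

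**4. Is the matching itself a problem?** No. The 16 were ranked on pre-test lactate, paired with their neighbour and randomised within pair (200,000 runs with no effect). The size of the correlation between pre-test lactate and change was set to 0 or to √((1 − r)/2) for assumed test-retest correlations r of 0.9, 0.7 and 0.5 with equal variances: √0.05 = 0.22, √0.15 = 0.39, √0.25 = 0.50.

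| Correlation size | 0 | 0.22 | 0.39 | 0.50 |
|---|---|---|---|---|
| Planned ANOVA, matching ignored | 5.0% | 4.5% | 3.6% | 2.7% |
| Adjusted for pre-test lactate | 5.0% | 4.9% | 5.0% | 5.0% |

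Ignoring the matching makes the test conservative, not anti-conservative. The harm comes from the missing random step and missing masking.

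**The case against.** The strongest reply is that this is silence, not a demonstrated flaw. Matching into pairs is compatible with a random draw within each pair, and the draw may have been made and not written down. There is a hint that text is missing: citations in the body jump from 28 to 31, and the skipped references are supplement trials, one of them double-blind and randomised. References 37 to 41 are also uncited, so the list may simply come from a longer manuscript. This objection stands as a limit on what can be claimed: the plan permits non-random, open groups and does not prove them. It does not supply the missing rule.

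The word placebo, and the statement that the comparator group followed the same protocol, suggest that participant masking was intended. So the open-group half of the concern is the weaker half. Still, no masking procedure is given for anyone.

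Lactate is read by instrument with a coefficient of variation of at most 1.5%, and the self-reported training impulse is not part of the primary aim. Both are true. What remains is effort in maximal bouts, which reaches lactate whatever the assay precision.

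Every bias size above is assumed, and moderate selection moves the error rate only to between 5.1% and 8.2%. That is correct, and the conclusion does not rest on those figures. Finally, this is a feasibility study of 16, which lowers the stakes, but its primary aim is still worded as a supplement effect.

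**Conclusion.** The concern holds. As written, the allocation rule can be followed exactly by hand-picking which member of each match gets the enzyme product, after all pre-test results are known and with everyone aware of the groups. A group by time difference could then not be securely attributed to the supplement, which is the primary aim. This needs correcting before the comparison is read as causal.

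The size of any bias is unknown. Under the stated assumptions it runs from negligible to a false-positive rate of 18.5% through selection alone, and 0.35 SD from any source is enough to double the nominal 5%. The lactate matching, the placebo arm, the pre/post comparison and the instrument-read outcomes reduce the risk but do not remove it.

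**What to change.** If a random draw and masking were used or planned, state how the sequence was made, who held it and who was masked. If neither was planned and allocation is still to come:

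- Name one pre-test lactate value for matching, rank the 16 on it and form 8 adjacent pairs.
- Assign enzyme or placebo within each pair from a computer-generated list made in advance and concealed from those who test.
- Issue coded containers and keep testers and the analyst unaware of the code until data lock. Acknowledge that taste and colour may still unmask participants.
- Adjust for the matching lactate. A paired analysis (7 df) or a randomisation test over the 2^8 = 256 allocations (smallest two-sided p = 2/256 = 0.0078) is optional.

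The methods are written in the past tense. If allocation has already been made and was not random, call the study a non-randomised comparison and limit causal wording.

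Separately, the comparator is maltodextrin in the design section and malt syrup in the Supplementation Protocol; the two must be reconciled.

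The cost is a list, someone outside testing to hold it, coded containers and a few sentences. There are no extra participants, visits or measurements. The covariate takes one degree of freedom (14 to 13). Simulated difference detectable with 80% power, in SD of change:

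| Correlation size | 0 | 0.22 | 0.39 | 0.50 |
|---|---|---|---|---|
| Planned ANOVA | 1.51 | 1.50 | 1.48 | 1.47 |
| Adjusted for lactate | 1.52 | 1.48 | 1.41 | 1.32 |
| Paired | 1.64 | 1.60 | 1.52 | 1.44 |

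The covariate loses almost nothing when lactate is unrelated to change and gains otherwise. The paired analysis loses power against the planned ANOVA up to at least 0.39 and never beats the covariate in this range.

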**Project Title: The Impact of Fruit and Vegetable Enzyme
Supplementation on Aerobic Capacity, and Blood
Biochemical Values Following Very Low Volume High-
Intensity Interval Exercise - Feasibility Study of Exercise
Design Using Motion-Sensing Video Games**

Study Protocol

File date : 15 / August / 2023

Introduction

Exercise represents a paradoxical element in health management, offering substantial benefits yet posing potential risks if not properly moderated [1, 2]. High-intensity exercise, while efficacious in improving various health parameters, can lead to oxidative stress, muscle damage, and inflammation [3, 4]. The oxidative stress primarily arises from increased reactive oxygen species production during intensive physical activities [5]. Moreover, exercise-induced fatigue serves as a protective mechanism against overexertion and consequent injuries [6, 7]. In contemporary fitness regimes, HIE, particularly the Tabata training method, has gained prominence for its effectiveness in enhancing aerobic power, fat oxidation, and muscular endurance [8-10]. These attributes are especially crucial for the elderly population, a demographic that significantly benefits from regular physical activity [11-13].

Exergaming, an innovative blend of physical exercise and interactive gaming, has emerged as a transformative approach to fitness, especially in engaging diverse age groups in regular physical activity. Its efficacy in enhancing key fitness parameters like aerobic capacity, agility, and coordination, coupled with its ability to make exercise more enjoyable, has been well documented [14-16]. This fusion of technology and exercise not only caters to the digital age but also opens avenues for personalized fitness experiences, adaptable to various demographic needs [17, 18]. While exergaming has been effective across a range of ages, its application in elderly populations presents unique opportunities and challenges. As the elderly population seeks safe, engaging, and effective exercise methods, exergaming could offer a solution that aligns with these requirements. However, integrating HIE concepts into exergaming for the elderly remains a relatively uncharted territory. HIE, known for its efficiency in improving cardiovascular health and metabolic function, could significantly benefit older adults, particularly in terms of enhancing functional capacity and overall quality of life [12, 19].

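### Does labelling 370 seconds as active exercise time distort the training-load analysis?

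*Combined protocol and SAP*

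**What the plan says.** The session is described twice in the combined protocol and SAP. *Participants And Experimental Design* gives eight 20-second sets of "maximum effort exercise with 30 seconds of complete rest between each set, resulting in a total exercise time of 370 seconds". *Exergaming HIEE Test-Combination Of Exergaming And HIEE* repeats the design: "The exercise protocol included eight sets of 20-second high-effort exercises, interspersed with 30-second rest intervals, totaling 370 seconds of active exercise time". The two agree on the number of sets, the length of each set, the length of each rest and the total. They differ only in what they call the total.

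Duration then appears in the definition of training load. *Training Impulse* introduces TRIMP as a quantity "which is calculated as the product of exercise intensity and duration" and sets out when ratings and heart rate are taken: "At the end of each exercise bout (8 bouts in total) and during the recovery period before the next bout (7 bouts in total"). Two versions of the load follow:

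- **Heart-rate version** (*% HRmax Calculation Method*): weights the minutes spent in each of five intensity zones, using a continuous record: "During the entire HIIE, the participant's HR was recorded every 5 seconds using a heart rate monitor".
- **Perceived-exertion version** (*RPE Calculation Method*): the instruction is to "calculate the exercise load by multiplying the RPE value of each exercise segment by the exercise time and summing them up".

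*Statistical Analysis* names training impulse, with lactate and heart rate, as a variable for the group-by-time mixed ANOVA.

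**The concern.** The rests are described as complete rest, so they cannot count as activity, yet the exergaming section counts them. A reader who took the label at face value would credit each participant with more than twice the exercise performed, in a study whose title advertises a very low volume of exercise.

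The sharper worry is the RPE load. Its formula multiplies a rating by a time in minutes, and the only totals that the document labels as exercise time are the two 370 s figures. If an analyst used that total as the multiplier for the bout ratings, the reported load would be too large. Because training impulse goes into the ANOVA, it is fair to ask whether a group comparison could be affected.

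**Working it through.** **Inputs.** Eight sets, 20 s per set and 30 s per rest come from both descriptions of the session. Seven rests follow from rest being taken between sets, and *Training Impulse* confirms this with its count of eight bouts and seven recoveries.

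**Reproducing 370 s.**

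- Exercise: 8 × 20 = 160 s = 160/60 = 2.67 min
- Rest: 7 × 30 = 210 s = 210/60 = 3.50 min
- Elapsed: 160 + 210 = 370 s = 370/60 = 6.17 min

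Two alternatives fail to match. Exercise alone gives 160 s, and a rest after every set, including the last, gives 160 + 8 × 30 = 400 s. The number is therefore exact as elapsed time, from the start of the first set to the end of the eighth.

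**Size of the mislabelling.** 370/160 = 2.31, an excess of 210 s. Exercise is 160/370 = 43.2% of the session and rest is 210/370 = 56.8%.

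**Does it enter the RPE load?** The instruction works by exercise segment and then sums. With 20-second sets, the natural form is

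load = Σ RPEᵢ × 20/60 over the eight bouts = (mean bout RPE) × 160/60.

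The total of 370 s does not appear, so the distortion factor on this reading is 1.00.

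**Worst case.** Suppose an analyst instead used (mean bout RPE) × 370/60. Every value, in both groups and at both tests, is then multiplied by the same c = 370/160 = 2.3125. The mean, SD and confidence limits are each multiplied by c. Every mean square is multiplied by c², so

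F = (c² × MS effect)/(c² × MS error) = MS effect/MS error,

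and the p-value is unchanged. Cohen's d is a difference divided by an SD. Both carry the factor c, so d is unchanged too.

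**Does it enter the heart-rate load?** The time in each zone comes from readings taken every 5 seconds over the whole session. No nominal duration is supplied to the formula, so the label has no route into it.

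**The case for a change.** The best case for a change is that the error is real, it sits in a defining feature of the session, and correcting it would cost a few words. Nowhere does the document state 160 s. The term exercise time serves both as a session total and as a multiplier, and the RPE section does not say which duration it means. It is also unstated whether the ratings taken during the seven recoveries enter the load. That matters because recovery ratings can differ between participants, so adding them would change what the variable measures and would not be a constant rescaling. The invariance of F, p and d shown above does not cover that case.

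Part of this stands. The word active is wrong, and the phrase in the design section is loose in the same way, although it can be read as session length. The question about recovery ratings is also open. It is a separate matter, however: it would remain exactly as it is if the label were corrected, and the wording by exercise segment already favours the bouts alone.

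The rest is weaker. Anyone repeating the session needs only the number of sets, the set length and the rest length, and the mislabelled sentence itself gives all three. The title sets no threshold in seconds that the 370 s figure could breach. Asking for confirmation that the heart-rate load covers the whole session adds nothing, since the text already says the recording does.

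**Conclusion.** The observation is correct but clerical. The session is fully and consistently specified, and its arithmetic closes exactly; one adjective is attached to the wrong total. A competent analyst following the segment-by-segment instruction would use 20 s per bout and never need 370 s. The effect on the RPE load is nil on that reading, and at most a uniform change of scale if the session total were applied to bout ratings. Either way, correcting the word would alter no test, p-value or effect size.

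This rests on two assumptions: that the same nominal duration applies to everyone at both tests, as the fixed session implies, and that the RPE load uses the bout ratings, as its wording suggests. Nothing in the document shows 370 s being used as a multiplier. The treatment of recovery ratings is missing detail that does not follow from this label and gives no reason to change the plan on this point.

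### Does the RPE training impulse need a stated rule on whether ratings taken during the rest intervals count?

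*Combined protocol and SAP*

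**What the plan says.** The RPE Calculation Method section obtains the load by "multiplying the RPE value of each exercise segment by the exercise time and summing them up", and its formula is a CR-10 "RPE score × exercise time (min"). It does not define a segment, and the formula has no index separating bouts from rests.

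The Training Impulse section collects ratings at the end of each of the 8 bouts and also "during the recovery period before the next bout (7 bouts in total), participants were asked to report their RPE". It then adds: "This process was repeated 8 times".

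Two places give a duration. Participants And Experimental Design describes "maximum effort exercise with 30 seconds of complete rest between each set, resulting in a total exercise time of 370 seconds". The Exergaming HIEE Test section describes the sets as "interspersed with 30-second rest intervals, totaling 370 seconds of active exercise time".

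For the heart-rate version, the % HRmax Calculation Method section records heart rate every 5 seconds, "During the entire HIIE", and scores it by zone: "The weighted score of each block was multiplied by the exercise time (min").

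Under Statistical Analysis, training impulse is one of three variables in the group by time mixed ANOVA, with 8 participants per group.

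**The concern.** Ratings are collected in the recovery periods, in the very section that introduces the load, but no sentence says what they are for. The protocol also attaches the word exercise to all 370 seconds, a total that can be reached only by counting the rests. An analyst who took that label literally could weight recovery ratings by 30 seconds each and add them in. That would be a different outcome variable, not a rescaled one, and rest would carry most of its time weight. With 8 per group, the two versions could fall on opposite sides of 5%. If the choice were left until the results were known, the nominal error rate would no longer hold.

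Two further points look untidy. Eight repetitions of a rating process that includes recovery do not match 7 recoveries. The heart-rate load also refers to exercise time without saying whether samples taken at rest count.

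**Working it through.** **The protocol's own figure.** Inputs: 8 sets of 20 s, with 30 s of rest between sets, hence 7 rests.

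- Work: 8 × 20 = 160 s = 2.67 min.
- Rest: 7 × 30 = 210 s = 3.50 min.
- Total: 160 + 210 = 370 s. The stated figure reproduces exactly and confirms 7 rests. Eight rests would give 160 + 240 = 400 s, which appears nowhere in the documents.

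**Three readings of the RPE load.**

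1. Bout ratings × 20 s each: maximum 10 × 2.67 = 26.7 AU.
2. Bout ratings spread over 370 s: reading 1 × 370/160 = 2.31 times as large for everyone. F, p and d are unchanged.
3. Bout and recovery ratings: maximum 10 × 6.17 = 61.7 AU. Rest share of time weight = 210/370 = 56.8%.

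Only reading 3 alters the test. The 57% is a share of time, not of the score. With an assumed bout rating of 8 (8 × 2.67 = 21.3 AU), a rest rating of 3 adds 10.5 AU, 33% of the total. A rest rating of 5 adds 17.5 AU, or 45%. The share reaches 57% only if rest is rated as hard as work. A rating of 0, the scale's anchor for rest in Table 2, adds nothing.

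**Effect on power.** The documents give no RPE data, so every input here is assumed: two-sided 5%, 14 df, noncentrality 2d (from √(8/2) = 2), and correlation ρ = 0 / 0.5 / 0.8 between the changes in mean bout rating and mean recovery rating. With k the ratio of the recovery SD to the bout SD, an effect on bout ratings alone is multiplied in reading 3 by

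160 / √(160² + (210k)² + 2ρ·160·210k).

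| Case | ρ = 0 | ρ = 0.5 | ρ = 0.8 |
|---|---|---|---|
| Factor, k = 1 | 0.61 | 0.50 | 0.45 |
| Power in reading 3, d = 1.5 on bouts only, k = 1 | 40% | 28% | 25% |
| Same, k = 0.5 | 65% | 49% | 43% |
| Same, k = 2 | 17% | 14% | 13% |
| Power in reading 3, d = 1.5 on both ratings, k = 1 | 97% | 89% | 84% |

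Reading 1 has 79.7% power at d = 1.5. So reading 3 loses power if only bout ratings respond and gains it if both do. The protocol's threshold for a large effect is 0.8. At that size reading 1 has noncentrality 1.6 and power of 32%, so the test is weak whichever score is used.

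**Effect on type I error.** Simulated changes with no effect (8 v 8, bivariate normal, equal SDs, 200,000 trials per ρ; a t-test on changes equals the group by time F when there are two time points):

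- Each score used alone: 5.0%.
- Whichever score is significant: 8.8% / 7.8% / 6.8%.
- The two scores disagree on significance: 7.7% / 5.5% / 3.6% of trials.

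**Heart-rate load.** 370/5 = 74 samples, of which 160/5 = 32 fall in bouts and 210/5 = 42 in rests. The maximum is 5 × 2.67 = 13.3 AU from bouts only, or 5 × 6.17 = 30.8 AU from all samples. Recording runs through the whole test for the stated purpose of calculating % HRmax, which points to using all samples.

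**The case for a change.** The best argument for a change is that the plain reading is not the only one the text supports. The protocol twice presents 370 s as exercise time, both load formulas use that term, and the recovery ratings are described only under Training Impulse. Two competent analysts could therefore compute different scores for a variable that is tested. Writing the rule down would need no new measurement.

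Part of this stands. The term is undefined, and calling 370 s active time is wrong by the protocol's own figures. But the label does not bring recovery ratings into the sum. Taken literally as a multiplier of bout ratings it leads to reading 2, which gives the same test. To reach reading 3 an analyst must also treat an interval described as complete rest as a segment of exercise. Moreover, Figure 2, whose legend marks when heart rate and RPE are taken, and the cited sources for the RPE method are not visible here. It therefore cannot be said that nothing available to the trial team settles the matter.

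**Conclusion.** No change to the plan is needed. This is an undefined term that an analyst would fill sensibly: the RPE load is the sum over the eight bouts, and a written rule would only record that reading. It gives one score and one test at 5%. The choice between 160 s and 370 s affects the units alone.

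The remaining discrepancies are clerical. The 370 s is 160 s of work plus 210 s of rest, and the arithmetic behind it is correct. The phrase about eight repetitions is loose wording beside the explicit counts of 8 and 7. For heart rate, recording throughout the test already suggests the rule.

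The alarming magnitudes are conditional. The fall in power from 80% to between 25% and 40% rests on d = 1.5, an effect on bout ratings only, and equal SDs. It is milder or worse at other SD ratios, and it reverses if both ratings shift, so the direction is unknown. The 7% to 9% type I error requires calculating both scores and selecting on the result; the missing definition does not produce it by itself. Training impulse is also not named in the primary aim, which concerns aerobic capacity and blood lactate.
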